7.3.4 ADVERSE EVENT REPORTING

See above

7.3.5 SERIOUS ADVERSE EVENT REPORTING

Any AEs will be reported in the Emory REDCap computerized database, within 15 days of the event and any SAEs will be reported to the Emory IRB within 24-48 hours of the event. The standard Emory IRB reporting guidelines for AE and SAE reporting will also be followed. The investigators and staff will enter all AEs into the REDCap database, and evaluate the SAEs, in close coordination with the Emory IRB. The investigators and staff will track and summarize AE frequency, severity, and relatedness at a frequency appropriate to ensure subject safety.

A periodic (annual unless otherwise specified) report of AEs with a frequency > 5% will be provided for this clinical trial 1-2 months prior to IRB annual review. The Emory IRB reporting guidelines for UP, AE and SAE reporting should also be followed.

7.3.6 REPORTING EVENTS TO PARTICIPANTS

Not applicable

7.3.7 EVENTS OF SPECIAL INTEREST

Risks include local infection, inflammation, lightheadedness, pain or discomfort, bleeding at the CGM insertion site, bruising, itching, scarring or skin discoloration, hematoma (also known as a black and blue mark) caused by the leakage of blood under the skin, CGM Sensor or needle breakage during insertion, wear or removal.

Sensors may fracture or be retained in situ on rare occasions. In these rare instances when this has occurred in the past, consulting physicians and surgeons have recommended not to remove the wire fragment from beneath the skin as long as there are no symptoms of infection or inflammation. In the event that signs and/or symptoms of infection or inflammation arise such as redness, swelling, and pain participants should consult with the investigator or prescribing physician for the best course of action. If there is no portion of the broken sensor wire fragment or retained sensor wire visible above the skin, attempts to remove it without medical guidance are not advised. Include content in this section if applicable, otherwise note as not-applicable.

Describe any other events that merit reporting to the sponsor, study leadership, IRB, and regulatory agencies. For example, in oncology trials, secondary malignancies are often captured.

Include any other reportable events not already included in the previous sections, such as cardiovascular and death events, medical device incidents (including malfunctions), laboratory test abnormalities, and study intervention overdose.

7.3.8 REPORTING OF PREGNANCY

Pregnancy will be an exclusion criterion. Pregnancy test will be performed prior to study procedures and thereafter at investigator's discretion. Women of childbearing age will be considered pregnant as demonstrated by a positive β HCG PT (Pregnancy Test) to be performed during study visits (blood draw) per investigator discretion. Investigators will follow Emory IRB protocol for reporting.

7.4 UNANTICIPATED PROBLEMS

Unanticipated Adverse Events (UAE) are defined as any adverse experience that is not identified in nature, severity or frequency in the general investigational plan or elsewhere in the current application.

An unanticipated adverse device effect (UADE) is not expected to occur. An UADE is defined as any serious adverse effect on health or safety or any life-threatening problem or death caused by – or associated with – the device, if that effect, problem, or death was not previously identified in nature, severity, or degree of incidence in the investigational plan (including documents such as the protocol, the informed consent document, other study-related documents), or any other unanticipated serious problem associated with the device that relates to the rights, safety, or welfare of participants.

During the review of a reported SAE, if Clinical Affairs management with the Investigator input determines the severity or extent of the event was not cited in this protocol or associated protocol materials, and the event was classified as, 'possibly related' to the device, the event will be documented as an UADE. If the event is classified as an UADE, the Investigator must notify the IRB within fifteen (15) working days of the original SAE notification.

If determined that the UADE presents an unreasonable risk to participants, the investigators will terminate all investigations or parts of investigations presenting that risk as soon as possible, but not later than 5 working days after such determination is made and not later than 15 working days after IRB first receives notice of the original SAE.

7.4.1 UNANTICIPATED PROBLEM REPORTING

The investigator will report unanticipated problems (Ups) to the reviewing Institutional Review Board (IRB). The UP report will include the following information:

- Protocol identifying information: protocol title and number, PI's name, and the IRB project number;
- A detailed description of the event, incident, experience, or outcome;
- An explanation of the basis for determining that the event, incident, experience, or outcome represents an UP;
- A description of any changes to the protocol or other corrective actions that have been taken or are proposed in response to the UP.

7.4.2 REPORTING UNANTICIPATED PROBLEMS TO PARTICIPANTS

Participants will be informed about Ups on an individual level by the study team.

8 STATISTICAL CONSIDERATIONS

8.1 STATISTICAL HYPOTHESES

For Aim 1a, we will summarize mean daily glucose, incidence of hypoglycemia, glycemic variability measures separately using CGM data and POC BG data and compare them

(between CGM vs. POC – as available) by using paired t-tests or Chi-square tests (or Fisher's exact tests, for incidence of hypoglycemia). Using CGM data, we will further compute and summarize the incidence of asymptomatic, and nocturnal CGM-detected hypoglycemia (<70 mg/dL, < 54 mg/dL and equal to 40 mg/dL), overall time in hypoglycemia (< 70 mg/dL, < 54 mg/dL), time (%) in target range (70-180 mg/dL) and time (%) in hyperglycemia (>180 mg/dL, >250 mg/dL), 10-90% glucose percentiles, and mean hourly interstitial glucose before, during and after dialysis.

For Aim 1b, we will assess the accuracy of CGM based on paired CGM and POC data or paired CGM and YSI data. We will calculate the overall MARD, as well as MARD stratified according to different glucose ranges (e.g. MARD for glucose <70, 70-180, >180, >250 mg/dL). We will also employ Clarke Error Grid and Surveillance Error Grid methods to determine the clinical accuracy of Dexcom G6 as compared to the reference values from POC or YSI. The statistical analyses for **Aim 1** are mostly about calculating summary statistics for different glycemic control measures and accuracy measures. For the continuous primary outcome of Aim 1a, with a sample size of 40, the length of the confidence interval for the continuous outcome would be 0.64 times its standard deviation. There would be over 80% power to detect a mean difference equals to 0.46 times the standard deviation of the continuous outcome based on a two-sided paired t-test with alpha = 0.05.

For Aim 2, the primary outcome is percentage time in hypoglycemia range (glucose <70 mg/dL, as measured by CGM, see definitions above) during the last 10 days of each study phase. The study design for Aim 2a is a two by two cross-over design. To assess the effect of real-time (RT) CGM on the primary outcome, we will first compare the changes in percentage time in hypoglycemia range from the first study phase to the second study phase between the two randomization groups (i.e. intervention-control vs. control-intervention), using a nonparametric Wilcoxon-test. Such a test is equivalent to testing the difference in the primary outcome between the intervention of RT-CGM and the usual care of POC under the assumption that the carryover effects are the same for the two randomization groups. To estimate the effect of RT-CGM vs usual care of POC, we will further fit a nested three-way linear mixed model which appropriately accommodates the two by two cross-over study design while accounting for the effects of study phase and sequence of intervention and usual care. For continuous secondary outcomes, we will follow the same analysis plan presented for the primary outcome. For binary secondary outcomes (e.g. the incidence of hospitalization), we will compare the discrepancy in the binary outcome between the two study phases using logistic regression. We can further fit a generalized linear mixed model tailored to the two by two cross-over design to estimate the effect of CGM vs. POC on the binary secondary outcomes.

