Primary Endpoint:

Mean daily glucose, as measured by CGM and POC BG

Secondary Endpoints:

Incidence of hypoglycemia by POC BG and CGM (< 70 mg/dl), glycemic variability [% coefficient of variability (%CV)], mean amplitude of glucose excursions (MAGE)], rates of asymptomatic, and nocturnal CGM-detected hypoglycemia (<70 mg/dl, < 54 mg/dl and equal to 40 mg/dl), % time in hypoglycemia (< 70 mg/dl, < 54 mg/dL), time (%) in target range (70-180 mg/dl) and time (%) in hyperglycemia (>180 mg/dL, >250 mg/dl), 10-90% glucose percentiles, and mean hourly interstitial glucose before, during and after dialysis

Aim 1b. To assess the accuracy of the CGM system, as determined by differences in mean absolute relative difference (MARD), compared to time-matched paired glucoses measured by POC BG (standard of care) and YSI 2900 analyzer glucose sample in patients with DM2 on dialysis

Primary Outcome: Mean absolute relative difference (%MARD, calculated as the average relative difference between CGM, POC BG and intra-dialysis YSI matched glucose pairs).

Secondary Outcomes: %MARD for glucoses <70 mg/dL, <54 mg/dL, 70-180 mg/dL, >180 mg/dL, >250 mg/dL, % MARD during non-dialysis and during dialysis hours. Proportion of CGM values within $\pm 20\%$ or ± 20 mg/dL (%20/20) of reference glucose values <70 mg/dL, <100 mg/dL, >100 mg/dL and >250 mg/dL, and the analogous %15/15, %30/30. We will utilize the Clarke Error Grid (CEG) and Surveillance Error Grid (SEG) analysis to evaluate for clinical risk of CGM errors

AIM 2. To determine the efficacy of real-time CGM in preventing hypoglycemia among insulin-treated patients with DM2 on hemodialysis, compared to standard of care (POC BG)

Primary Outcomes: Differences in mean percentage time-in-hypoglycemia (< 70 mg/dL) during the intervention phase, compared

to control in both groups (i.e. intervention-control vs. control-intervention).

Secondary Outcomes: CGM-measured % time-in-range (70-180 mg/dL), % time in hypoglycemia (<54 mg/dL), % time in hyperglycemia (>180 mg/dL, >250 mg/dL), % coefficient of variation (%CV, MAGE), HbA1c, hospitalization or emergency room visits for hypoglycemia or diabetes ketoacidosis.

Endpoints:

See above for each study aim

Study Population:

Adult patients with type 2 diabetes on hemodialysis will be identified, recruited, and consented from the dialysis units of Emory Dialysis Centers and Grady Healthcare.

Phase:

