4 STUDY DESIGN

4.1 OVERALL DESIGN

Aim 1a. To examine overall glycemic control, as measured by CGM and POC (standard of care, as available), among ESRD patients with DM2 treated with insulin. In this longitudinal cohort study, we will examine the overall glycemic control among insulin-treated patients receiving hemodialysis.

Hypothesis: Patients with DM2 on hemodialysis will have wide glycemic excursions, characterized by increased rates of symptomatic and asymptomatic hypoglycemia, with subsequent rebound hyperglycemic excursions and overall high glycemic variability.

Aim 1b. To assess the accuracy of the CGM system, as determined by differences in mean absolute relative difference (MARD), compared to time-matched paired glucoses measured by POC BG (standard of care) and YSI 2900 analyzer glucose sample in patients with DM2 on hemodialysis. In this comparative study, we will analyze glucoses obtained by CGM to the reference glucoses obtained by home POC BG and YSI obtained during dialysis sessions among subjects participating in Aim 1a.

Hypothesis: We hypothesize that the overall accuracy in patients with DM on dialysis will be within <12% MARD, compared to the standard of care POC BG and YSI .

Study Overview/Procedures for Aim 1a and Aim 1b:

In this prospective observational cohort study, we will determine daily glucose concentration, rates of hypoglycemia (overall, nocturnal and asymptomatic), hyperglycemia and GV measures detected by real-time CGM in patients treated by maintenance dialysis compared to POC BG (standard-of-care, as available). Up to 100 subjects could be recruited, until a total of 40 insulin-treated patients with DM2 on hemodialysis have completed all procedures for this Aim. After obtaining informed consent (Aim 1a), we will collect baseline demographics, and available laboratory data from the electronic medical record and place a blinded CGM (Day 1) for 10 days. Subjects will complete a food record for three (3) days for caloric intake analysis, one (1) on a pre-dialysis day, one (1) on dialysis day and one (1) the day after a dialysis day⁶⁵. No therapy adjustment or interventions will be made by the study team during this period. Glycemic monitoring and treatment of dysglycemia will be performed by the primary care team following standard-of-care.

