Study Design: The study team will perform pre-screening on subjects scheduled for their nephrology visits and will approach potential candidates by phone to determine interest and further qualification. If potential candidate expresses interest and qualifies for study participation, full consent procedure will be conducted during/after their hemodialysis sessions. After providing informed consent, patients will have a sensor inserted by the study team (Day 1, Visit 1). Insertion of the CGM sensor will be performed per manufacturer instructions and following an aseptic technique. After insertion of the sensors, providers will ensure proper hemostasis is achieved. Sensors will be removed if prolonged bleeding or severe pain occurs. Patients will be educated on study procedures and on sensor, transmitter and receiver care. Subjects will be

instructed to perform self-monitored blood glucose four times daily at home during the study duration (10 days), and to complete a DM diary (diabetic medications, SMBG – as available-, food record, etc.) as well as to complete a Food record for three (3) days, one (1) on a pre-dialysis day, one (1) on dialysis day and one (1) the day after a dialysis day. Subjects will use their dialysis-validated glucose meter^{15,66} and supplies, per standard of care. Subjects will be asked to complete a one (1) time 8-point SMBG between days 5-9 days after CGM insertion. For the 8-point SMBG, the study will provide a glucose meter with test strips (Nova Stat Strip). This is the glucose meter currently used at all Emory Hospitals.

For Aim 1b: In addition, a dialysis circuit venous blood sample (0.5 ml) for BG will be collected during one hemodialysis session as follows: at initiation, then every thirty (30) minutes, until the end of the dialysis session by the dialysis nurse, assisted by the study team. Samples from the circuit will be analyzed on the YSI 2300 glucose analyzer (visit 2). Similarly, capillary POC glucoses will be obtained at the same times, using the Nova Stat Strip glucose meter. CGM sensors that fail within the first 24 hours will be replaced, and the study will start again on Day 1 after re- insertion. On day 10, the CGM will be removed, and data download into Dexcom software (Visit 3). Glucose data glucoses from POC, venous testing will be paired with glucoses from the CGM (closest following value within 5 minutes). Food records will be collected.

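### Aim 1a compares hypoglycaemia incidence by CGM and by POC in the same patients with tests for independent groups (secondary endpoint)

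*Combined protocol and SAP*

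**What the plan says.** Section 8.1 says that mean daily glucose, incidence of hypoglycaemia and glycaemic variability will be summarised separately from CGM and from POC data, then compared between the methods "by using paired t-tests or Chi-square tests" ("or Fisher's exact tests, for incidence of hypoglycemia"). McNemar's test, conditional logistic regression and mixed models are not mentioned for Aim 1.

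The synopsis (section 1.1) lists "Incidence of hypoglycemia by POC BG and CGM", at a threshold of 70 mg/dL, as an Aim 1a secondary endpoint.

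Section 4.1 shows that both methods are applied to the same people at the same time. The team will "place a blinded CGM (Day 1) for 10 days", and the same subjects are "instructed to perform self-monitored blood glucose four times daily at home during the study duration (10 days"). The comparison is with POC only where it exists: "compared to POC BG (standard-of-care, as available").

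For Aim 2, section 8.1 does look within patients for binary outcomes: it will "compare the discrepancy in the binary outcome between the two study phases using logistic regression" and may add a generalised linear mixed model suited to the cross-over. The omission is therefore specific to Aim 1a.

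**The concern.** If each patient is classed as having or not having hypoglycaemia by each method, the data form one paired 2×2 table: both methods, CGM only, POC only, neither. The information on a difference lies in the two discordant cells. Chi-square and Fisher see only the two marginal totals and assume that they come from different people. They return the same p-value however closely the methods agree within patients.

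The two methods follow the same patient's glucose, so positive agreement is the natural expectation. The independent-groups variance is then too large, the true type I error falls below 5%, and a real excess of hypoglycaemia detected by CGM can be missed. That excess is what the protocol's rationale in sections 2.1 and 2.2 predicts, since it argues that fingerstick testing overlooks asymptomatic and nocturnal episodes.

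**Working it through.** **The plan's own figures.** Section 8.1 gives precision and power only for the continuous primary outcome, and both reproduce at n = 40.
- Confidence interval length: 2 × t(0.975, 39)/√40 = 0.640 SD (stated 0.64).
- Power of a two-sided paired t-test at 0.46 SD, noncentral t with 39 df and noncentrality 0.46 × √40: 81.0% (stated over 80%), taking the SD as that of the paired difference.

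No size or power figure is given for the incidence comparison.

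**Inputs for the incidence comparison.**
- n = 40 completers (section 4.1); two-sided alpha 0.05.
- POC incidence 50%: section 2.3.1 expects about half of those recruited to have hypoglycaemia by POC, without giving a time window.
- CGM incidence and within-patient correlation (phi): not in the documents, so assumed and varied.

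**Why the size moves.** Let p be the common incidence under the null hypothesis. The variance of the difference between the two proportions is 2p(1−p)(1−phi)/n. Chi-square uses 2p(1−p)/n. Its size is therefore roughly 2 × [1 − Φ(1.96/√(1−phi))]: about 1.9% at phi 0.3 and 0.6% at phi 0.5.

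**Exact calculation.** For incidences p1 and p2, the probability that both methods are positive is p1·p2 + phi·√[p1(1−p1)p2(1−p2)]. All paired tables of 40 patients were enumerated with their multinomial probabilities. Chi-square (no continuity correction) and Fisher were applied to the margins as 40 against 40, and McNemar to the discordant pairs.

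| True rates, POC vs CGM | phi | Chi-square | Fisher | Mid-p McNemar |
|---|---|---|---|---|
| 50% vs 50% (type I error) | −0.3 | 9.5% | 6.2% | 4.4% |
| | 0 | 5.7% | 3.3% | 4.6% |
| | 0.1 | 4.4% | 2.5% | 4.7% |
| | 0.2 | 3.3% | 1.7% | 4.7% |
| | 0.3 | 2.3% | 1.1% | 4.5% |
| | 0.5 | 0.7% | 0.3% | 4.1% |
| 50% vs 70% (power) | 0 | 46% | 37% | 42% |
| | 0.3 | 45% | 34% | 57% |
| | 0.5 | 43% | 31% | 72% |
| 50% vs 80% (power) | 0 | 82% | 75% | 80% |
| | 0.3 | 86% | 79% | 93% |

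Asymptotic McNemar behaves much like mid-p (type I error 4.6% and power 57% for 50% vs 70% at phi 0.3). The exact version is conservative (2.7% and 48% in the same two cases).

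**Worked example.** Suppose 12 of 40 patients have hypoglycaemia by POC and 20 of 40 by CGM. The pooled proportion is 32/80 = 0.4 and the difference 0.2, so chi-square = 0.2²/(0.4 × 0.6 × 2/40) = 3.33 and p = 0.068. Fisher gives p = 0.110. Neither changes with agreement. The mid-p McNemar result does:

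| CGM only : POC only | phi | Mid-p McNemar p |
|---|---|---|
| 8 : 0 | 0.65 | 0.004 |
| 10 : 2 | 0.44 | 0.022 |
| 12 : 4 | 0.22 | 0.049 |
| 14 : 6 | 0 | 0.078 |

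**The case against.** Several points can be made for leaving the text alone.

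- **Chi-square might loosely mean McNemar's chi-square.** This is unlikely, because the alternative offered is Fisher's exact test, the small-sample counterpart of the independent-groups test. If McNemar was meant, the text still has to say so.
- **The unit of analysis is not defined.** The plan says only incidence. If readings, days or episodes were counted, the problem would be clustering within patients and the error could run the other way. This stands as a limit on the stated direction. The per-patient reading is the natural one, and section 2.3.1 speaks of the share of individuals, but the plan should state it.
- **The direction depends on agreement.** At phi −0.3 chi-square is anti-conservative (9.5%). McNemar keeps its level there too (4.4%), so the remedy is right either way.
- **Equal rates are not expected, and a large difference would be found anyway.** This is partly right. At 50% vs 80% and phi 0.3, chi-square already has 86% power. The loss matters for moderate differences and for agreement beyond the weak range; at phi 0.1 the size of chi-square is still 4.4%.
- **Missing POC data are partly handled.** Section 5.4 makes failure to perform SMBG a screen failure for Aim 1, and the 40 must complete all procedures. The as-available wording still leaves the analysed set open.
- **The stakes are low.** The endpoint is secondary, section 8.1 describes Aim 1 as mainly descriptive, and no sample size or decision rests on this p-value. This stands, and it limits the weight of the point without removing it.

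**Conclusion.** The concern holds. The tests named for the incidence comparison do not fit the paired design, and no paired binary test is named for Aim 1.

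With 40 patients and one yes/no result per patient per method, moderate agreement (phi 0.3 to 0.5) cuts the true type I error to between 2.3% and 0.7% for chi-square, and between 1.1% and 0.3% for Fisher. For 50% vs 70%, relative to mid-p McNemar, it costs about 12 to 29 percentage points of power with chi-square (57 − 45; 72 − 43) and 23 to 41 with Fisher (57 − 34; 72 − 31).

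These sizes rest on an assumed CGM incidence and an assumed positive correlation. They shrink when agreement is weak, and the power loss is smaller when the difference is large. The consequence is a loss of sensitivity on one secondary endpoint. The primary comparison of means, its stated precision and power, and Aim 2 are untouched. The point should be fixed, but nothing else in the plan turns on it.

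**What to change.** In section 8.1:

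1. Replace chi-square and Fisher for the CGM-versus-POC incidence comparison with McNemar's test, mid-p or asymptotic.
2. Report the difference in proportions with a paired confidence interval, together with the full paired 2×2 table.
3. Define the outcome for each patient and method as any value below 70 mg/dL, yes or no.
4. Restrict this comparison to patients with both CGM and POC data, and report how many are left out.

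This takes a line or two of wording for the test and a short definition of the outcome and analysed set, with no new data. Two small costs follow. If the methods turn out to be uncorrelated within patients, mid-p McNemar has slightly less power than chi-square (42% against 46% for 50% vs 70%). Patients without POC data drop out of this one comparison.
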